13.1.1. Incidence of Treatment-Emergent Adverse Events

Treatment-Emergent Adverse Events and TEAEs reported for at least 3% and 5% of patients in either treatment group will be summarized. For the Summary of TEAE reported for at least 3% and 5% of patients in either treatment group, it will be only presented with relationship to study drug.

All TEAEs will be flagged in the listing for AEs described in [Section 13.1](#).

13.1.2. Adverse Event Leading to Death

All patients who have an outcome of AE as ‘Death’ will be only listed including following information: SOC, PT, verbatim term, cause of death, date of death, days from the first dose until death, date of last visit, days on study and relationship to study drug.

13.1.3. Serious Adverse Events

A serious adverse event (SAE) is defined as any event that results in death, is immediately life threatening, requires inpatient hospitalization or prolongation of existing hospitalization, results in persistent or significant disability/incapacity, important medical event based on appropriate medical judgment or is a congenital anomaly/birth defect.

If a patient is hospitalized purely for convenience, the hospitalization does not qualify as an SAE. If a patient is hospitalized solely due to disease progression, the hospitalization does not qualify as an SAE.

All SAEs will be listed including variables detailed in [Section 13.1](#). Additional information of SAE will also be provided based on the ‘Serious Adverse Event’ page of eCRF.

13.1.4. Treatment-Emergent Adverse Events leading to Permanent Study Drug Discontinuation

All TEAEs which led to permanent discontinuation of study drug will be summarized and listed including variables detailed in [Section 13.1](#).

13.1.5. Treatment-Emergent Adverse Events of Special Interest

The following will be considered as AEs of special interest: infusion-related reactions (IRR), infections and progressive multifocal leukoencephalopathy (PML).

TEAEs of IRR will be determined if the information is recorded as IRR in the ‘Adverse Events’ page of the eCRF. TEAEs of infections will be determined if a SOC is ‘Infections and infestations’. Although PML is an AE of special interest, it is captured only by a PT ‘Progressive multifocal leukoencephalopathy’. Therefore, TEAEs of PML will be included in the summary of TEAEs instead of generating an additional table.

All TEAEs of IRR and infections will be listed separately including variables detailed in [Section 13.1](#). With variables detailed in [Section 13.1](#), the listing will include information recorded on the ‘Adverse Events’ and ‘Infusion related/Anaphylactic Reaction’ page of eCRF will be included: start/stop time of IRR; signs and symptoms; whether symptoms are experienced (no, yes with

specified intensity NCI CTCAE); the lowest blood pressure (BP) level after study drug exposure [mmHg] and date/time of BP assessment (if BP is decreased after study drug exposure); comments on IRR.

13.2. Clinical Laboratory Evaluations

Clinical laboratory assessments of hematology, clinical chemistry and urinalysis will be performed at the local laboratory. Since reported units and normal ranges are various among sites, results will be converted to standard unit. Results of the assessment will be collected at the time points specified in the [APPENDIX 1](#).

Descriptive statistics for actual values and changes from baseline of each hematology or clinical chemistry parameter will be presented by visit for the Safety population.

All possible numeric parameters will be labeled and graded by CTCAE. Grades that require clinical input only will not be evaluated. Grades which are part numeric and part clinical input will be assigned based on the numeric portion only. CTCAE terms and ranges for applicable parameters are listed in [APPENDIX 3](#). The CTCAE grades for this analysis will be Grade 1 (Mild), Grade 2 (Moderate), Grade 3 (Severe) and Grade 4 (Life-threatening). The CTCAE Grade 5 (Death) will not be applied in this analysis since death cannot be determined from a numeric laboratory result. If the result for a patient does not satisfy any CTCAE grade, it will be classified as “No Grade”.

Results of unscheduled visits will be included for CTCAE grade. In summary, unscheduled visit and EOT visit results will be used in the related cycle. For example, C1D5 (Day 5 of Cycle 1 result will be summarized in Cycle 1; EOT1 result will be summarized in the last cycle of the Induction Study Period. In addition, C2D1 result should be summarized in Cycle 1 result because laboratory blood sample for C2D1 is taken before Cycle 2 dose administration. The same rule will be applied to subsequent cycles.

The number and percentage of patients who have a result for each grade will be summarized by laboratory category, CTCAE term, visit, grade and treatment group for the Safety population and Safety population – 2nd Maintenance Period subset. The summary will be presented in Overall and by each study period (up to MP1, MP2). Only the most severe case during unscheduled and scheduled visits will be included.

The number and percentage of patients with CTCAE grade greater than or equal to 3 will be summarized by laboratory category, CTCAE term, grade and treatment group for the Safety population and Safety population – 2nd Maintenance Period subset. The summary will be presented in Overall and by each study period (up to MP1, MP2). Only the most severe case of the post-baseline during unscheduled and scheduled visits will be included.

The number and percentage of patients with CTCAE grade will be provided, by laboratory category, CTCAE term, grade and treatment group for the Safety population and Safety population – 2nd Maintenance Period subset, in the form of a shift table to detect changes from baseline. The summary will be presented in Overall and by each study period (up to MP1, MP2). Only the most severe case during unscheduled and scheduled visits will be included for the post-baseline result.

All hematology and clinical chemistry data will be listed by treatment group. Results of CTCAE will be presented by separate listing.

Result interpretation for all urinalysis parameters will be collected as {'Normal', 'Abnormal, not clinically significant' and 'Abnormal, clinically significant'}. The number and percentage of patients with urinalysis results will be provided, by parameter, visit and treatment group for the Safety population, in the form of a shift table to detect changes from baseline.

All urinalysis data will be listed by treatment group, visit and parameter.

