APPENDIX 3: Table of CTCAE Terms and Grades

CTCAE Term	Laboratory Parameter	Level	Grade 1	Grade 2	Grade 3	Grade 4
Anemia	Hemoglobin	Low	<LLN - 10.0 g/dL; <LLN - 100 g/L	<10.0 - 8.0 g/dL; <100 - 80g/L	<8.0 g/dL; <80 g/L;	-
Alanine aminotransferase increased	Alanine Aminotransferase (ALT)	High	>ULN - 3.0 x ULN	>3.0 - 5.0 x ULN	>5.0 - 20.0 x ULN	>20.0 x ULN
Alkaline phosphatase increased	Alkaline phosphatase	High	>ULN - 2.5 x ULN	>2.5 - 5.0 x ULN	>5.0 - 20.0 x ULN	>20.0 x ULN
Aspartate aminotransferase increased	Aspartate Aminotransferase (AST)	High	>ULN - 3.0 x ULN	>3.0 - 5.0 x ULN	>5.0 - 20.0 x ULN	>20.0 x ULN
Blood bilirubin increased	Total Bilirubin	High	>ULN - 1.5 x ULN	>1.5 - 3.0 x ULN	>3.0 - 10.0 x ULN	>10.0 x ULN
Creatinine increased ¹	Creatinine	High	>1 - 1.5 x baseline; >ULN - 1.5 x ULN	>1.5 - 3.0 x baseline; >1.5 - 3.0 x ULN	>3.0 baseline; >3.0 - 6.0 x ULN	>6.0 x ULN
Hemoglobin increased ¹	Hemoglobin	High	Increase in >0 - 2 gm/dL above ULN or above baseline if baseline is above ULN	Increase in >2 - 4 gm/dL above ULN or above baseline if baseline is above ULN	Increase in >4 gm/dL above ULN or above baseline if baseline is above ULN	-
Hypercalcemia	Calcium	High	>ULN - 11.5 mg/dL; >ULN - 2.9 mmol/L	>11.5 - 12.5 mg/dL; >2.9 - 3.1 mmol/L	>12.5 - 13.5 mg/dL; >3.1 - 3.4 mmol/L	>13.5 mg/dL; >3.4 mmol/L
Hyperkalemia	Potassium	High	>ULN - 5.5 mmol/L	>5.5 - 6.0 mmol/L	>6.0 - 7.0 mmol/L	>7.0 mmol/L
Hypernatremia	Sodium	High	>ULN - 150 mmol/L	>150 - 155 mmol/L	>155 - 160 mmol/L;	>160 mmol/L

Hyperuricemia	Uric Acid	High	>ULN - 10 mg/dL (0.59 mmol/L) without physiologic consequences	-	>ULN - 10 mg/dL (0.59 mmol/L) with physiologic consequences	>10 mg/dL; >0.59 mmol/L
Hypoalbuminemia	Albumin	Low	<LLN - 3 g/dL; <LLN - 30 g/L	<3 - 2 g/dL; <30 - 20 g/L	<2 g/dL; <20 g/L	-
Hypocalcemia	Calcium	Low	<LLN - 8.0 mg/dL; <LLN - 2.0 mmol/L	<8.0 - 7.0 mg/dL; <2.0 - 1.75 mmol/L	<7.0 - 6.0 mg/dL; <1.75 - 1.5 mmol/L	<6.0 mg/dL; <1.5 mmol/L
Hypoglycemia	Glucose	Low	<LLN - 55 mg/dL; <LLN - 3.0 mmol/L	<55 - 40 mg/dL; <3.0 - 2.2 mmol/L	<40 - 30 mg/dL; <2.2 - 1.7 mmol/L	<30 mg/dL; <1.7 mmol/L
Hypokalemia	Potassium	Low	<LLN - 3.0 mmol/L	<LLN - 3.0 mmol/L	<3.0 - 2.5 mmol/L	<2.5 mmol/L
Hyponatremia	Sodium	Low	<LLN - 130 mmol/L	-	<130 - 120 mmol/L	<120 mmol/L
Neutrophil count decreased	Total Neutrophils	Low	<LLN - 1500/mm ³ ; <LLN - 1.5 x 10 ⁹ /L	<1500 - 1000/mm ³ ; <1.5 - 1.0 x 10 ⁹ /L	<1000 - 500/mm ³ ; <1.0 - 0.5 x 10 ⁹ /L	<500/mm ³ ; <0.5 x 10 ⁹ /L

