Platelet count decreased	Platelet count	Low	<LLN - 75,000/mm ³ ; <LLN - 75.0 x 10 ⁹ /L	<75,000 - 50,000/mm ³ ; <75.0 - 50.0 x 10 ⁹ /L	<50,000 - 25,000/mm ³ ; <50.0 - 25.0 x 10 ⁹ /L	<25,000/mm ³ ; <25.0 x 10 ⁹ /L
White blood cell decreased	White Blood Cells	Low	<LLN - 3000/mm ³ ; <LLN - 3.0 x 10 ⁹ /L	<3000 - 2000/mm ³ ; <3.0 - 2.0 x 10 ⁹ /L	<2000 - 1000/mm ³ ; <2.0 - 1.0 x 10 ⁹ /L	<1000/mm ³ ; <1.0 x 10 ⁹ /L

Note: The LLN and ULN values will be the normal ranges as provided by the local laboratory at each relevant transfer.

1 The most severe grade is counted if the CTCAE grade is discrepant by multiple definitions

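### Numeric-only laboratory grading gives hyperuricemia Grades 1 and 3 the same range with no tie-break marked; separately, the hypokalemia Grade 1 and 2 cells need checking

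*SAP*

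**What the plan says.** SAP 13.2 grades every laboratory parameter that can be graded numerically, using the ranges in Appendix 3. Two sentences deal with criteria that are not purely numeric. The first is "Grades that require clinical input only will not be evaluated". The second is "Grades which are part numeric and part clinical input will be assigned based on the numeric portion only".

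Appendix 3 defines hyperuricemia Grade 1 as ">ULN - 10 mg/dL (0.59 mmol/L) without physiologic consequences" and Grade 3 as ">ULN - 10 mg/dL (0.59 mmol/L) with physiologic consequences". Grade 2 is a dash, and Grade 4 is anything above 0.59 mmol/L. In the hypokalemia row, the Grade 1 and Grade 2 cells both read "<LLN - 3.0 mmol/L", with no clinical wording in either.

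Footnote 1 to Appendix 3 reads "The most severe grade is counted if the CTCAE grade is discrepant by multiple definitions". Its marker stands on creatinine increased and hemoglobin increased only. For the by-grade summary, SAP 13.2 adds "Only the most severe case during unscheduled and scheduled visits will be included". A further table covers patients with "CTCAE grade greater than or equal to 3 will be summarized by laboratory category, CTCAE term, grade and treatment group", and shift tables and a separate CTCAE listing are also planned.

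**The concern.** A grading rule should give one laboratory value one grade. For uric acid between ULN and 0.59 mmol/L the written rule gives two, and they are far apart: SAP 13.2 labels Grade 1 as mild and Grade 3 as severe. Two programmers working from the same text could produce different tables. The SAP plans two study reports, so an unwritten choice could also differ between them.

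The two possible errors are not equally serious. If the lower grade is taken, the hyperuricemia Grade 3 line is simply empty. If the higher grade is taken, every uric acid value above ULN up to 0.59 mmol/L enters the Grade 3-or-higher table under a severity label that depends on physiologic consequences, which the numeric analysis does not look at.

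**Working it through.** There is no plan figure to reproduce. The check compares the ranges, counts what is affected, and follows the consequence through the tables.

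**1. Which terms have two grades with one range?** Inputs: the numeric portions of all rows of Appendix 3.

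- Terms: 19. Cells: 19 × 4 = 76.
- Cells printed as a dash: 5 (Grade 4 for anemia, hemoglobin increased and hypoalbuminemia; Grade 2 for hyperuricemia and hyponatremia). Defined cells: 76 − 5 = 71.
- Terms with clinical wording: 1 (hyperuricemia). As printed, the numeric-only rule therefore acts on this term alone.
- Terms in which two grades share an identical range: 2, namely hyperuricemia (Grades 1 and 3) and hypokalemia (Grades 1 and 2). Cells involved: 2 + 2 = 4 of 71.

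**2. Test values.** ULN and LLN come from local laboratories and are not in the documents, so a range was assumed.

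| Test | Assumed limits (mmol/L) | Value (mmol/L) | Grades met |
|---|---|---|---|
| Uric acid | ULN 0.36, 0.42, 0.45 | 0.46, 0.50, 0.59 | 1 and 3 |
| Uric acid | same | 0.60 | 4 only |
| Potassium | LLN 3.4, 3.5, 3.6 | 3.3, 3.0 | 1 and 2 |
| Potassium | same | 2.9 | 3 only |
| Potassium | same | 2.4 | 4 only |

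The result is the same under every assumed limit.

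**3. Does another rule settle it?** Footnote 1 would, but it is not marked on either term. The most-severe-case sentence is worded as a choice among scheduled and unscheduled visits, not between two grades for one result.

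**4. Effect on the Grade 3-or-higher table.** It is split by grade. Possible lines: 19 for Grade 3, plus 19 − 3 = 16 for Grade 4, which makes 35. Only the hyperuricemia Grade 3 line depends on the choice: 1 of 35. The hypokalemia overlap lies below Grade 3 and does not reach this table.

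Let n be the patients in an arm whose worst post-baseline uric acid lies in the shared range, and m those above 0.59 mmol/L.

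| Convention | Grade 1 | Grade 3 | Grade 4 |
|---|---|---|---|
| Lower grade | n | 0 | m |
| Most severe grade | 0 | n | m |

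The documents do not give n. For scale only: if all 87 patients planned per arm (SAP 5.2) were in the Safety population, each such patient would move the line by 1/87 = 1.1 percentage points.

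**5. Effect on the other outputs.** In the shift table, a patient with no grade at baseline and a later value in the shared range moves either to Grade 1 or to Grade 3. The by-grade tables and CTCAE listing change in the same way for uric acid. For potassium they change between Grades 1 and 2.

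**The case against.** The strongest reply is that the SAP does lean one way. The most-severe-case sentence can be read as counting each patient once at the worst grade met, and footnote 1 shows the same habit of mind. A programmer could reasonably default to Grade 3. This stands as a plausible reading, and it is why the point says that no tie-break is marked for the term, not that none could be inferred. It does not remove the problem, because that default is the one that fills the Grade 3 line with unassessed values.

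A reader might go further and infer that the SAP instructs this overcounting. It does not: footnote 1 is marked on two other terms, and the sentence in 13.2 speaks of visits.

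A reader might also infer the opposite, that the sentence on clinical-input-only grades already removes hyperuricemia Grade 3. That does not hold either. The cell has a numeric portion, so the sentence that follows governs it.

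Hypokalemia needs separate care. Its duplication does not come from the numeric-only rule, since neither cell carries clinical wording. It would be tempting to say that Grade 2 should be a dash, but the documents do not show which cell is wrong, and a fault in reading the PDF table cannot be fully excluded.

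Three further replies stand. Lower versus most severe grade is partly a matter of convention. The table shells are a separate addendum that was not available and may specify the grading or layout; the 35-line count assumes the layout described in 13.2. Finally, the cell and line counts describe table slots, not patients.

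**Conclusion.** The hyperuricemia point holds: under the numeric-only rule, one uric acid value above ULN and up to 0.59 mmol/L meets two grades, and the tie-break footnote is not marked on the term. This rests on the ranges and footnote markers as printed, and on local ULN values below 0.59 mmol/L. The hypokalemia duplication is a row to verify, not a demonstrated error in a particular cell.

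Severity is minor. The effect is confined to descriptive laboratory outputs: the by-grade, Grade 3-or-higher and shift tables, and the CTCAE listing. Grade 4 counts, summaries of raw values and all efficacy results are unaffected. The number of patients is unknown, so nothing here supports a claim that the safety comparison between arms would be distorted; whichever convention is chosen would apply to both arms.

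**What to change.** For the numeric laboratory analysis, print a dash for hyperuricemia Grade 3 in Appendix 3, so that values in the shared range count as Grade 1. Add a note that uric acid rises with physiologic consequences are captured through adverse event grading, which SAP 13.1 already bases on CTCAE 4.03. The dash is a convention that Appendix 3 uses in five cells now; defined cells go from 71 to 71 − 1 = 70. If the sponsor prefers the most severe grade, footnote 1 should be marked on the term and the Grade 3 line labelled as numeric only.

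For hypokalemia, check the row against CTCAE 4.03, then either correct it or state which single grade a numeric value in that range takes.

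Both changes should be made before programming. The cost is one table cell, one note and one row check, with no new data. The downside is that the numeric tables will show no Grade 3 hyperuricemia.

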13.2.1. Hematology

Following hematology laboratory tests will be included: Absolute neutrophil count (*10E9/L), Hemoglobin (g/dL), Platelet count (*10E9/L) and White blood cell count (*10E9/L).

13.2.2. Clinical Chemistry

The following chemistry laboratory tests will be included: Alanine aminotransferase (ALT) (U/L), Albumin (g/L), Alkaline phosphatase (U/L), Aspartate aminotransferase (AST) (U/L), Blood urea nitrogen (mmol/L), Calcium (mmol/L), Creatinine (μ mol/L), Glucose (mmol/L), Lactate dehydrogenase (IU/L), Potassium (mmol/L), Sodium (mmol/L), Total bilirubin (μ mol/L), Total protein (g/L) and Uric acid (mmol/L).

13.2.3. Urinalysis

All relevant categorical urinalysis parameters will be included: Bilirubin, Blood, Glucose, Ketones, and Protein. Microscopic examination of Bacteria count, Red blood cell count and White blood cell count will be done if urinalysis dipstick results for any of the analytes are 2+ or greater.

13.3. Immunogenicity

Blood samples for assessment of immunogenicity (Anti-drug antibodies [ADA] and Neutralizing antibody [NAb]) will be collected at the time points specified in the [APPENDIX 1](#). Immunogenicity assessment consists of both ADA and NAb assay.

The ADA assay will be performed using the single labelled antibody with CT-P10 tag. NAb will

be determined using a single antibody.

The ADA assay will follow three tiered approach consisting of (i) screening assay, (ii) specificity/confirmatory assay and (iii) titration. The test outcome for the screening assay will be: {'Potential Positive' or 'Negative'}. Samples that are 'Potential Positive' in the screening assay will be spiked with excess study drug to determine if samples are a true positive. The test outcome for the specificity/confirmatory assay will be: {'Reactive', 'Negative', or 'N/A'}. 'Reactive' indicates a true positive test outcome and will be labeled as 'Positive' in outputs, 'Negative' is considered negative, and 'N/A' indicates the assay was negative at the screening phase of the process. Patients with a 'Negative' test outcome for either the screening or specificity/confirmatory assay will be considered 'Negative' for the overall ADA assessment. For further characterization, the antibody level will be assessed by titration in confirmed positive samples.

Samples that are positive in the ADA assay will be analyzed further to conduct a NAb assessment. The test outcome for the screening assay will be: {'Reactive', 'Rejected for Hemolysis (HEM)', 'Insufficient Sample Volume (ISV)' or 'Negative'}. Samples that are 'Reactive' in the screening assay will be undergone further testing in the confirmatory (immunodepletion) assay to determine if samples are a true positive. The test outcome for the confirmatory assay will be: {'Positive', 'Negative' or 'N/A'}. 'Positive' indicates a true positive test outcome, 'Negative' is considered negative, and 'N/A' indicates the assay was negative at the screening phase of the process. Patients with a 'Negative' test outcome for either the screening or confirmatory assay will be considered 'Negative' for the overall NAb assessment. For further characterization, the antibody level will be assessed by titration in confirmed positive samples.

Both ADA and NAb test will be performed on samples obtained at all relevant visits. The results of the final ADA assay and the final NAb assay will be summarized. The number and percentage of patients will be provided by treatment group and visit for the Safety population.

The ADA and NAb titer values of the CT-P10 tagged assay will be transformed using a $[\log_2 X] + 1$ and $[\log_8 X]$ transformation respectively. If the values in the data are forms of inequality, the sign of inequality will be removed and then the values will be transformed. Descriptive statistics of transformed ADA titer will be displayed by treatment group and visit for the Safety population.

All immunogenicity test results including actual and transformed results of ADA/NAb titer will be listed by treatment group and visit.

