Male or female patients and their partners who have been surgically sterilised for less than 6 months prior to the first administration of the study drug must agree to use 1 medically acceptable method of contraception or practice true abstinence during study treatment. Menopausal females must have experienced their last period more than 12 months prior to study entry (ie, when the informed consent form [ICF] is signed) to be classified as not of childbearing potential.

For both premenopausal women and women who are less than or equal to 12 months after the onset of menopause, patient has a negative serum pregnancy test during the Screening Period.
8. Patient has adequate bone marrow, hepatic, and renal function reserve as evidenced by:
 - Haemoglobin level of \geq 10 g/dL
 - Absolute neutrophil count of \geq 1500/mm³
 - Platelet count of \geq 100 000/mm³
 - Total bilirubin level of \leq 2.0 mg/dL
 - Aspartate aminotransferase and alanine aminotransferase levels of \leq 3 times the ULN for the reference laboratory (\leq 5 \times ULN for the reference laboratory with known hepatic involvement by lymphoma)
 - A serum creatinine level of \leq 1.5 \times ULN for the reference laboratory, or a calculated creatinine clearance by the Cockcroft-Gault equation of \geq 50 mL/min
9. Patient is able to understand verbal and/or written instructions and comply with all study requirements.
10. Patient is informed, given ample time and opportunity to read and/or understand about participation in the study, and has signed and dated the written ICF.

Exclusion Criteria:

Patients meeting any of the following criteria will be excluded from the study:

1. Patient has received rituximab (or a rituximab proposed biosimilar product).
2. Patient has allergies or hypersensitivity to contrast agents for radiograph, murine, chimeric, human or humanised proteins.
3. Patient has evidence of histological transformation to high-grade or diffuse large B-cell lymphoma.
4. Patient has known central nervous system involvement or any evidence of spinal cord compression by lymphoma.
5. Patient has received previous treatment for NHL:
 - Previous treatment including chemotherapy, radiotherapy, immunotherapy, and/or surgery (except previous biopsy).
 - All doses of corticoid therapy for treatment of NHL.

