5.4.1.1. Intent-to-treat Population – ADA Negative/Positive Subset

For analyses of efficacy primary endpoint, the ITT population – ADA negative subset will be defined consisting of all patients in the ITT population who have only “Negative” result in immunogenicity anti-drug antibody (ADA) test obtained after receiving at least one dose (full or partial) of study drug and up to Maintenance Cycle 3 (up to 7 months), including unscheduled visit result. Other patients in the ITT population who show at least one “Positive” result in ADA tests obtained after receiving at least one dose (full or partial) of study drug and before Maintenance Cycle 3 will be considered as ITT population – ADA positive subset.

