13.6. Electrocardiogram

A 12-lead ECG will be performed at the time points specified in the [APPENDIX 1](#). All scheduled 12-lead ECGs must be performed after the patient has rested quietly for at least 5 minutes in the supine position.

Findings will be classified as {‘Normal’, ‘Abnormal, not clinically significant’ and ‘Abnormal, clinically significant’}. The number and percentage of patients will be provided, by treatment group and visit for the Safety population, in the form of a shift table to detect changes from baseline. All ECG data will be listed by treatment group and visit.

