17. HBsAg, HBsAb, and HBcIg should be assessed within 42 days before the first drug administration in all patients (mandatory). If the result is HBsAg (positive), the patient should be excluded from the study. For patients whose HBsAg is negative, HBsAb is negative or positive, and HBcIg is positive, a DNA test should be performed within 42 days before the first drug administration. If the DNA test result is positive, the patient should be excluded from the study and if the DNA test result is negative, the patient can be included. For the patients enrolled based on the DNA test, the DNA test will be done every 24 weeks (± 8 weeks) for monitoring purposes until the patient receives new anticancer therapy. If hepatic symptoms are suspicious (ie, AST ≥ 3 times the ULN, ALT ≥ 3 times the ULN, or total bilirubin ≥ 2 times the ULN) during the Induction Study Period and Maintenance Study Period, then HBsAg, HBsAb, HBcIg, and DNA should be tested. Hepatitis C virus antibody and HIV antibody must be obtained within 42 days before the first study drug administration for all patients. Hepatitis and HIV testing will be performed at the local laboratory.
18. Immunoglobulin (IgG, IgM, IgA) testing and immunogenicity (antiriximab antibodies) testing will be obtained prior to the beginning of study drug of the Induction Study Period. Immunoglobulin testing will also be obtained at the EOT1 visit and before administration on Day 1 of Cycle 1 (Month 3; EOT2), Cycle 2 (Month 5), and Day 1 of Cycle 3 (Month 7) during the Maintenance Study Period. Immunogenicity testing will also be obtained prior to Day 1 of Cycle 1 (Month 3; EOT2), Cycle 3 (Month 7), and Cycle 6 (Month 13) and Cycle 9 (Month 19) during the Maintenance Study Period and at the EOT3 visit. Immunoglobulin and Immunogenicity testing must be completed before administration of the study drug at each planned visit and any time during the EOT visit. Immunoglobulin and Immunogenicity testing will be performed at the central laboratory. If a patient is terminated within 6 months from Day 1 of Cycle 1 of Induction Study Period, immunogenicity should be assessed at EOT2 (Month 3), EOT3 and the first follow-up visit.

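### The ADA analysis never links a patient's post-dose results to the pre-dose sample, so antibodies that predate study drug are not separated from drug-induced ones

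*SAP*

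**What the plan says.** SAP 13.3 labels a sample positive when it is reactive in the confirmatory assay, without reference to any earlier sample from the same patient. The planned summary is: "The number and percentage of patients will be provided by treatment group and visit for the Safety population". For titre it is: "Descriptive statistics of transformed ADA titer will be displayed by treatment group and visit for the Safety population". All ADA and neutralising-antibody results are also listed.

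The baseline information exists. Appendix 1, footnote 18, says that immunogenicity "testing will be obtained prior to the beginning of study drug of the Induction Study Period", and Appendix 2 shows the same pre-dose sample at Induction 1. Section 5.5 defines baseline as the last value before first dosing. Confirmed positives are titrated.

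Section 5.4.1.1 builds the ITT ADA-positive subset from patients with at least one positive test "obtained after receiving at least one dose (full or partial) of study drug and before Maintenance Cycle 3". Section 5.4.2.1 does the same for the per-protocol population. Neither looks at the pre-dose result.

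The protocol synopsis excludes patients who have already received rituximab or a proposed biosimilar of it (exclusion criterion 1).

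**The concern.** A patient who is positive before the first infusion and unchanged afterwards counts as positive at every later visit and enters the ADA-positive efficacy subset. By design, neither study drug nor earlier rituximab explains that antibody. The Induction 1 row shows how many patients were positive at the start. Counts by visit cannot show whether the later positives are the same patients or new ones.

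The SAP makes this distinction elsewhere. Section 13.1 treats an adverse event as treatment-emergent if it was absent before exposure or was present and worsened; the ADA counterpart is induced plus boosted. ECG findings are shown "in the form of a shift table to detect changes from baseline", as are urinalysis, laboratory grades and physical examination. Immunoglobulins (13.4) get changes from baseline. ADA gets neither, although immunogenicity of CT-P10 in comparison with Rituxan is part of a secondary objective (SAP 3.2).

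At stake are the clarity and precision of a secondary safety comparison and the reading of a supportive efficacy subset.

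**Working it through.** **No figure to reproduce.** The plan states no ADA rate, pre-existing or induced, and no precision for the ADA comparison. Its power figures (91% ITT, 86% per-protocol) concern response rate and do not enter here.

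**Inputs.**
- From SAP 5.2: 87 patients per arm, 174 in total.
- Assumed: pre-existing rate *r* of 0%, 2%, 5% or 10%, equal in both arms; every pre-existing positive stays positive and none is boosted.
- Assumed: induced rate *d*, among patients negative at pre-dose, of 5% in one arm and 10% in the other.

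**Formulas.**
- Post-dose positive rate: p = 1 − (1 − r)(1 − d)
- Difference between arms: p₂ − p₁ = (1 − r)(d₂ − d₁)
- Standard error: √{[p₁(1 − p₁) + p₂(1 − p₂)]/87}

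Example at r = 5%: p₁ = 1 − 0.95 × 0.95 = 9.75%; p₂ = 1 − 0.95 × 0.90 = 14.50%; difference 4.75 points; SE = √[(0.0880 + 0.1240)/87] = 4.9 points.

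| Pre-existing | Positive, arm 1 | Positive, arm 2 | Difference (points) | SE (points) | Difference/SE |
|---|---|---|---|---|---|
| 0% | 5.00% | 10.00% | 5.00 | 4.0 | 1.26 |
| 2% | 6.90% | 11.80% | 4.90 | 4.4 | 1.11 |
| 5% | 9.75% | 14.50% | 4.75 | 4.9 | 0.96 |
| 10% | 14.50% | 19.00% | 4.50 | 5.7 | 0.80 |

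The difference loses 2% to 10% of its size. Most of the harm is added noise.

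**What linking recovers.** Count only induced positives, (1 − r)d, over all patients. At r = 5% the rates are 4.75% and 9.50%, the difference is still 4.75 points, and the SE is √[(0.0452 + 0.0860)/87] = 3.9 points, a ratio of 1.22. At 2% and 10% the ratios are 1.24 and 1.19. With pre-dose-negative patients as the denominator, the difference returns to 5.00 points (at r = 5%, about 83 per arm, SE 4.1 points). The gap stays at about 1.2 to 1.3 standard errors throughout, so the comparison is imprecise in any case.

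**Subset make-up.** In an arm with 5% pre-existing and 5% induced, 0.05/0.0975 = 51% of post-dose positives carried antibody before any drug. Sections 10.1.1 and 5.4.1.1 together also make the reporting rule depend on this. The ADA-positive subset is not summarised at 5% or less of the population, which is 0.05 × 174 = 8.7 patients. With 3% pre-existing and 3% induced in both arms, the subset holds (0.03 + 0.97 × 0.03) × 174 = 10.3 patients and is reported. The induced patients alone number 0.97 × 0.03 × 174 = 5.1.

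**The case against.** The strongest reply is that little is lost. The pre-dose visit is its own row, titre is shown by visit, and every result is listed by patient, so each positive patient's sequence can be read off. The table shells are a separate addendum not available here. A confirmatory tier precedes any positive label, and prior rituximab is excluded, so a high pre-dose rate is far from certain. The ADA subsets can be defended as asking whether antibody detected on treatment affects response, whatever its origin. Patients positive only before dosing are already outside the positive subset.

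Most of this stands, and it limits the size of the point. It does not supply a planned patient-level comparison. Reconstruction from listings would be unplanned, and any titre-rise cut-off might be chosen after results are known.

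A reader might also infer that pre-existing antibodies largely hide a real difference, since under the same assumptions a doubling shows as a ratio of 1.71, 1.49 or 1.31 at 2%, 5% or 10% pre-existing. The SAP plans no ratio, test or confidence interval for ADA, only percentages, and on that scale the loss is 0.1 to 0.5 points. Nor do the documents support calling the ADA subsets wrongly defined: they are not described as treatment-induced, and the definition is a choice of question.

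**Conclusion.** The point holds as a reporting gap that is cheap to close. The planned tables cannot separate pre-existing from drug-induced ADA within patients, and the ADA-positive subsets contain both without showing which is which.

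The size depends on a pre-dose rate that the documents do not give. At 0% there is no effect. At 2% to 10% with full persistence, a 5-point gap shows as 4.9 to 4.5 points, and its standard error rises from 4.0 to between 4.4 and 5.7 points. Full persistence is the unfavourable case for noise and for subset make-up; lower persistence reduces both.

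A reader might infer a systematic bias between arms, or doubt about the similarity claim. Neither follows. Randomisation balances pre-existing ADA in expectation, so dilution and chance imbalance are what remain. The primary ITT test of response rate uses no ADA result.

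**What to change.** In SAP 13.3, add one patient-level table by arm that places each patient in one class:

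- treatment-induced: pre-dose negative, at least one post-dose positive;
- treatment-boosted: pre-dose positive, with a titre rise above a cut-off that the sponsor sets from assay performance before unblinding;
- pre-existing and not boosted;
- negative;
- pre-dose missing, shown separately and not counted as induced.

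Compare arms descriptively on induced plus boosted, and give induced also as a percentage of pre-dose-negative patients. The cut-off rule should say how titres reported as inequalities are treated, because 13.3 removes the sign before transformation.

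Keep the by-visit table and the subsets in 5.4.1.1 and 5.4.2.1. Flag baseline-positive patients within the ADA-positive subset, or show them separately, for example through a supportive repeat on the induced-plus-boosted class.

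The cost is SAP wording, one extra table and a cut-off to pre-specify. No new samples are needed. Counts will be small, and the supportive subset may be too small to interpret.
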